Primary outcomes	
Primary outcomes assessed at T2 (change from baseline):
 
(i) Exercise mindset using the Mindset about the Process of Health – Exercise scale. This one-factor scale was developed and validated¹ to assess mindset about the process of engaging in physical activity (e.g., physical activity is difficult/easy, unpleasant/pleasurable, boring/fun). The scale consists of 7 items and is measured on a 4-point scale and scored from 1 to 4, with a higher score reflecting a more appeal-focused mindset about exercise
 
(ii) Osteoarthritis mindsets using the Illness Mindset Inventory. The Illness Mindset Inventory measures three mindsets about the nature and meaning of illness: that it is a catastrophe, manageable, or an opportunity. The scale consists of 20 items measured on a 6-point scale and scored from 1 to 6, with 10 of those questions capturing mindsets about chronic illness. The extent to which a participant endorsed each mindset was obtained by calculating the respective mean scores. A higher score indicates greater agreement with the mindset. This Illness Mindset Inventory is valid and reliable in individuals with knee osteoarthritis². We adapted the scale to focus on mindsets about "knee osteoarthritis" as opposed to "chronic disease."
 
Primary outcomes assessed at T3 (change from baseline):
 
(i) Knee pain using the question, "What was your average osteoarthritis-related pain over the past week?" and measured on an 11-point Numeric Rating Scale (NRS) from 0 (no pain at all) to 10 (the worst pain imaginable)
 
(ii) Physical activity using the Physical Activity Scale for the Elderly (PASE). The PASE asks respondents about the frequency of light, moderate, and strenuous work and leisure activities and is a validated measure of self-reported physical activity for individuals with osteoarthritis³. The scale is scored from 0 to 793 with higher scores indicating higher levels of physical activity.

Secondary Objectives	
Key secondary	Secondary outcomes assessed at T2 (change from baseline):

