We will randomize 505 individuals aged ≥ 45 years with knee osteoarthritis into one of three groups with 1:1:1 group allocation: the Mindset Group (participants receive a digital mindset intervention to improve mindsets about osteoarthritis and exercise), the Education Group (Participants receive a series of osteoarthritis education videos and reflective questions that matches the digital mindset intervention in duration and attention), or the No-Intervention Group (participants take the same surveys as the other groups at the same time points, but do not receive any additional content). Participants will complete an initial baseline survey and be randomized one week later. Those randomized to the Mindset and Education Groups will have one week to complete the self-paced online programs. All groups complete osteoarthritis knowledge and mindset surveys at this timepoint. One-month later, participants will receive a follow-up questionnaire.

Study Setting

The study will be conducted entirely online.

Eligibility Criteria

Inclusion Criteria:

- Over 45 years of age
- Self-reported doctor's diagnosis of knee osteoarthritis OR meets the National Institute for Health and Care Excellence osteoarthritis clinical criteria (activity-related knee pain and no knee morning stiffness lasting ≥ 30 minutes)
- Knee pain for at least 3 months
- Ability to walk unaided
- Can read and write in English
- Consistent internet access
- Willingness and ability to comply with the study requirements

Exclusion criteria:

- Past total knee arthroplasty or scheduled surgical procedure on any back or

- lower limb with osteoarthritis within the next 12 months
- Recent serious injury (within the past 2 months) on the knee(s) with osteoarthritis
- Any condition making it unsafe to participate in physical activity
- Intra-articular therapy within the past 6 months (e.g. injections such as corticosteroids and hyaluronic acid)
- Participates in physical exercise for 30 minutes or more 5 days per week

Interventions

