The efficacy of the mindset intervention will be deemed successful if enhancements in either or both key outcomes, namely pain intensity (NRS) or physical activity levels (PASE), are observed. Anticipating modest effect sizes between the mindset and educational cohorts, we conducted a preliminary power analysis, similar to prior online education studies for knee osteoarthritis^{12,13}, using G*Power 3.1 with a presumed effect size of 0.3 (see below). This analysis involved comparing the mindset group against both the education and no-intervention groups, leading to four distinct comparisons. These assessments are planned to be executed at a 5% significance level, aiming for an 80% probability of discerning a noticeable improvement in delta. Based on Boswell et al.⁷, we estimated the standard deviations for PASE and pain at 70.28 and 1.67, respectively. A 26-point difference in PASE was selected as the target delta. While no clinically significant benchmarks for PASE has been established, the intervention's focus on promoting walking and moderate exercise led us to define this delta as the equivalent shift in walking and light exercise frequency from “seldom” (<1 hour per day) to “sometimes” (1-2 hours per day), as per the PASE scale, giving a goal of 26 points. This determination necessitates a sample size of 139 participants per group, totaling 417. To compensate for an anticipated 20% dropout rate, we plan to enroll 501 participants. This sample size is adequately powered to detect a clinically relevant difference of 2 points in NRS pain¹⁴.

A priori power analysis

[name]

11/29/2022

Let, y_i^b represents outcome at baseline and y_i^f represents outcome at follow-up for i^{th} person in treatment group, and \bar{y}^b and \bar{y}^f represents respective means. Similarly, x_i^b represents outcome at baseline and x_i^f represents outcome at follow-up for i^{th} person in control group, and \bar{x}^b and \bar{x}^f represents respective means.

Assumption: Let $x_i^f - x_i^b \sim \mathcal{N}(\Delta_1, \sigma^2)$ and $y_i^f - y_i^b \sim \mathcal{N}(\Delta_2, \sigma^2)$.

Let's say $\Delta = \Delta_2 - \Delta_1$, we want to test the hypothesis

$$H_0 : \Delta = 0$$

$$\text{v/s } H_1 : \Delta > 0$$

Under H_0 , $T = (\bar{y}^f - \bar{y}^b) - (\bar{x}^f - \bar{x}^b) \sim \mathcal{N}(0, 2\sigma^2/n)$. We reject H_0 if $\frac{T}{\sqrt{2\sigma^2/n}} > z_{1-\alpha}$. We want n so that power at Δ is $1 - \beta$, i.e.,

[figure not shown]

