Statistical Methods

Statistical analysis will be carried out in R¹⁵ by a blinded statistician, [name], with no knowledge of group allocation.

Standard descriptive statistics will be presented for all participant characteristic measures at baseline. Prior to analysis, t-tests for continuous variables and chi-square (χ^2) tests for categorical variables will be conducted to test the equality of means of baseline characteristics. Additionally, baseline characteristic comparisons between participants who completed the study and those who dropped out will be reported.

Changes in primary and secondary mindsets post-intervention will be compared among the mindset intervention group versus the active attention control (education group) and the no-intervention control group. We will present standard descriptive statistics of and calculate changes from baseline to post-intervention for the mindsets and knee osteoarthritis knowledge and from baseline to one-month follow-up for all other outcome variables. Changes will be presented as the mean change with 95% confidence intervals, along with Cohen d, using the following formula:

$$cohen\ d = \frac{\bar{x}_2 - \bar{x}_1}{s}$$

where \bar{x}_2 denotes the mean of variable after intervention, \bar{x}_1 denotes the mean of variable before intervention, and s denotes the standard deviation of the change in the variable due to intervention.

We will perform the t-test to compare the change in outcome variables post-intervention and at follow-up between the mindset group and the education and no-intervention groups. We assume the equality of variance for the changes. The t-statistic is given by:

$$\frac{\bar{X} - \bar{Y}}{s_{pooled} \sqrt{\frac{1}{m} + \frac{1}{n}}}$$

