where \bar{X} is the mean of changes in the first group and \bar{Y} is the mean of the changes in the second group, s_{pooled} is the pooled standard deviation from the two groups. We assume that there were m people in the first group and n people in the second group. After calculating the t-statistics, the p-values will be computed to estimate the statistical significance of differences in changes between groups. We will perform Bonferonni correction for the four comparisons (e.g., the mindset group vs. the education group and the mindset group vs. the no-intervention group for pain and physical activity at one-month follow-up), which adjusts the significance threshold to $P = 0.0125$. The comparison of the education group to the no-intervention group will not be a primary comparison.

Data Monitoring

The trial coordinator will provide ongoing project oversight and will meet regularly with the senior investigators throughout the project period to provide study feedback including recruitment, retention, and adverse events. During the study, participants have access to email the study coordinator at any time to report adverse events.

Harms

The potential harms associated with this study include psychological complications resulting from the assessments or mindset and education programs or medical risks due to increasing physical activity levels. There is a small risk that individuals completing psychological questionnaires may become distressed, but there is no evidence of resulting psychological dysfunction. We performed pilot testing of the program and questionnaires in which there was no evidence of psychological complications or the risk of such complications. Further, while the program presents the benefits of physical activity, no specific programs are requested for participation and participants are encouraged to go slow and listen to their bodies.

Therefore, no harm or adverse events are foreseen in this study. However, if a complaint or adverse event arises, the research team will discuss and take appropriate action to manage the issue. Any serious adverse event or harm reported by participants will be recorded and reported.

Research Ethics Approval

The study protocol, consent form, and recruitment material will be approved by the Stanford University Research Compliance Office Institutional Review Board.

Protocol Amendments

Protocol amendments will be documented and reported.

Consent Or Assent

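### The between-group analysis is a t-test on change scores with no baseline covariate; adjusting for the baseline value of each outcome would be more precise and needs no new data.

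*Combined protocol and SAP*

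**What the plan says.** - **Statistical Methods.** The comparison of outcomes between arms, made with each of the two comparator arms in turn, is described as follows: "We will perform the t-test to compare the change in outcome variables post-intervention and at follow-up between the mindset group". The statistic is the two-sample t with a pooled standard deviation, on the stated footing that "We assume the equality of variance for the changes". Then: "After calculating the t-statistics, the p-values will be computed to estimate the statistical significance of differences in changes between groups". The four comparisons of pain and PASE at one month are judged at 0.0125 after Bonferroni correction. No regression, ANCOVA, mixed model or adjusted sensitivity analysis is planned. The other tests named there compare baseline characteristics, or completers with dropouts, and neither estimates a treatment effect.
- **Study Objectives (Table 2).** Outcomes are defined as changes, for example "Primary outcomes assessed at T3 (change from baseline" for pain and PASE.
- **Trial Design.** "Participants will complete an initial baseline survey and be randomized one week later". The baseline value therefore precedes allocation.
- **Missing Data.** Every survey item is forced-response, so anyone with a change score also has a complete baseline value.
- **Sample Size.** "A 26-point difference in PASE was selected as the target delta". The standard deviations are 70.28 (PASE) and 1.67 (pain), and the result is 139 per group. The appendix models sigma as the standard deviation of the change and tests a one-sided alternative.

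**The concern.** Subtracting baseline uses the baseline value, but with its coefficient forced to 1. If the true regression slope of follow-up on baseline is below 1, as it is for any rho below 1 when the two visits have equal spread, the change score over-corrects and carries variance that ANCOVA removes. In the realised sample the estimate then depends on whatever chance baseline difference the randomisation produced.

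What is at stake is precision on every continuous outcome: pain, PASE, the mindset primaries and the scale secondaries. It matters most for PASE, which sets the sample size and has no margin at the corrected threshold. The mindset primaries have no power statement, but the same variance ratio applies to them. The plan also tests baseline equality without saying what follows if a difference appears. Prespecified adjustment would settle that in advance.

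**Working it through.** **Inputs.** From Sample Size and its appendix: difference 26, sigma 70.279 (PASE) and 1.670 (pain), power 80%, one-sided alternative, 501 enrolled, 20% dropout. From Statistical Methods: alpha 0.0125 per comparison. Assumed: rho of 0.5, 0.7 or 0.9, equal standard deviation s at both visits, and 70.279 as the standard deviation of change. The analysis text does not state sidedness, so both are shown.

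**1. The plan's own figure.** The appendix formula is n = 2σ²(z₁₋α + z₁₋β)²/Δ². With one-sided alpha 0.0125 and 80% power:

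n = 2 × 70.279² × (2.241 + 0.842)² / 26² = 138.9, which rounds up to the plan's 139.

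**2. Variance ratio.** Var(change) = 2(1−ρ)s². The ANCOVA residual variance is (1−ρ²)s². The ratio is (1+ρ)/2, that is 0.75, 0.85 and 0.95 at rho 0.5, 0.7 and 0.9.

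**3. Completers.** 501 × 0.8 / 3 = 133.6, taken as 133 per arm.

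**4. Standard errors for PASE.** Change score: 70.279 × √(2/133) = 8.62. ANCOVA multiplies this by √((1+ρ)/2), giving 7.46, 7.95 and 8.40.

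**5. Power and interval width.** Power is noncentral t for 26 PASE points at alpha 0.0125, with one degree of freedom fewer for ANCOVA. Half-widths are for the 98.75% interval (critical value 2.515).

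| | Planned t-test | ANCOVA, ρ = 0.5 | ANCOVA, ρ = 0.7 | ANCOVA, ρ = 0.9 |
|---|---|---|---|---|
| Power, one-sided | 77.7% | 89.0% | 84.5% | 79.9% |
| Power, two-sided | 69.2% | 83.3% | 77.5% | 71.9% |
| Half-width, PASE points | 21.7 | 18.8 | 20.0 | 21.1 |
| Half-width, pain points | 0.52 | 0.45 | 0.47 | 0.50 |

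For pain, 2/1.670 = 1.20 standard deviations, and power is above 99.9% either way.

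**6. Simulation.** In a three-arm model (6000 trials per value of rho), ANCOVA power was 89.5%, 84.6% and 79.1% one-sided, and 84.3%, 77.4% and 71.0% two-sided. Both estimators averaged 25.8 to 26.1 for a true 26, so neither is biased.

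**7. Chance imbalance.** The standard error of the baseline difference is √(2/133) = 0.123 baseline SD. The baseline SD implied by 70.279/√(2(1−ρ)) is 70, 91 or 157. An imbalance of one standard error therefore moves the change-score estimate by (1−ρ) × SD × 0.123 = 4.3, 3.3 or 1.9 PASE points, which is 17%, 13% or 7% of 26. This is the loss of step 4 seen conditionally, not a further one: √(8.62² − 7.46²) = 4.3.

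**8. Unequal spread.** If the follow-up SD is k times the baseline SD, the ratio is k²(1−ρ²)/(1 + k² − 2ρk). At rho 0.5 and 0.7 this gives 0.87 and 0.97 for k = 1.2, and 0.57 and 0.63 for k = 0.8.

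**The case against.** The plan is coherent as it stands. Outcomes are defined as change, the power appendix models change, the test is on change, and 139 per group reproduces for exactly that test. Nothing the documents claim becomes false if the t-test stays. This is correct, and it is why the point is about efficiency only.

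The (1+ρ)/2 ratio needs equal spread at both visits. In general the change score loses precision when ρ × SD(follow-up)/SD(baseline) differs from 1. Step 8 shows the gain nearly vanishing in one case and growing in another. The documents give neither SD nor rho, so the size is uncertain. The direction is not: in large samples, with a common baseline slope across arms, ANCOVA is no less precise than the change score.

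The low starting power is not all due to the choice of test. Part comes from having 133 rather than 139 completers and part from unstated sidedness; at 139 and one-sided, power is 80%. Only the increment belongs here: about 11, 7 or 2 percentage points one-sided.

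The practical effect is limited, since success needs only one of pain and PASE, and pain is amply powered. That also stands. Finally, a three-arm model pools the residual variance over three arms instead of two. This extends the equal-variance assumption the plan already makes and should be stated in the SAP.

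**Conclusion.** The concern holds. The planned test is valid, but it gives up precision that the pre-randomisation baseline data would supply at almost no cost. With equal visit variances, the variance falls by 25%, 15% or 5% at rho 0.5, 0.7 or 0.9. For PASE at 133 per arm the planned test misses the 80% target under either sidedness. Adjustment reaches it one-sided at rho 0.5 and 0.7 (79.9% at 0.9), and two-sided at rho 0.5 only. For pain the benefit is a slightly narrower interval.

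The power figures rest on 70.28 being the standard deviation of change, as the appendix models it. If it is a single-visit value, they do not hold and only the variance ratio does. The existence of a gain is secure for any true slope that differs appreciably from 1; its size cannot be fixed from the documents. The change should be made, but the trial's validity does not depend on it.

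**What to change.** For pain, PASE and each other continuous outcome, replace the change-score t-test with a linear model of the follow-up value on arm (three levels) and the baseline value of that outcome. Using change as the response in the same model gives the identical arm differences, so the outcome definitions need not be altered. Report the adjusted Mindset minus Education and Mindset minus No-Intervention differences with confidence intervals, and keep 0.0125 for the four pain and PASE comparisons. State that the residual variance is pooled over the three arms. The within-arm mean changes with 95% intervals can stay as description. The multiple-selection symptom-management item is not continuous and falls outside this change.

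The cost is one degree of freedom per model, a short change to the SAP wording and one line of R per outcome. No new data are needed.

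### The pooled-SD t-test rests on an unsupported equal-variance assumption with no fallback; Welch's test would remove a small, conditional error at almost no cost, mainly in Mindset vs No-Intervention

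*Combined protocol and SAP*

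**What the plan says.** The Statistical Methods section compares change scores between Mindset and each of the other two arms with a two-sample t-test. It states "We assume the equality of variance for the changes", and the SD in the denominator "is the pooled standard deviation from the two groups", so pooling is done separately for each pair of arms. Arm sizes may differ: "We assume that there were m people in the first group and n people in the second group". Four tests (pain and PASE at one month, each against Education and No-Intervention) are judged at 0.0125 after Bonferroni correction. The a priori power analysis under Sample Size likewise uses one common variance for both arms.

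Three other sections bear on whether arm sizes and variances stay equal. Allocation is 1:1:1 through the Qualtrics randomizer, and no blocking is described. Under Missing Data, people who do not complete a survey are removed. Under Trial Design, "Those randomized to the Mindset and Education Groups will have one week to complete the self-paced online programs", while the No-Intervention arm only takes surveys.

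The plan gives no variance check, unequal-variance alternative or sensitivity analysis.

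**The concern.** The pooled t-statistic keeps its level when the two arms are the same size or have the same variance. It can lose it when both differ. If the smaller arm has the larger variance, the pooled standard error is too small and the test is too liberal. If the smaller arm has the smaller variance, the test is too conservative and gives away power.

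Both conditions are possible here. A self-paced program that changes behaviour in some people and not others adds spread to the Mindset change scores, and No-Intervention has no such source. The Mindset arm also has an extra task at which people can be lost. The comparison exposed is Mindset vs No-Intervention, for pain and for PASE. Because the plan counts improvement in either outcome as success, the level of each test matters.

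**Working it through.** **Inputs from the plan.** PASE target difference 26 and SD 70.28; per-test level 0.05/4 = 0.0125; 501 enrolled, so 501/3 = 167 per arm; 20% overall dropout.

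**Assumed, because the documents do not give them.** Dropout by arm, SD ratio by arm, and a two-sided test.

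**The plan's own figure.** Its formula is n = 2σ²(z₁₋α + z₁₋β)²/Δ². With one-sided α = 0.0125 and 80% power, n = 2 × 70.28² × (2.241 + 0.842)² / 26² ≈ 138.9, so 139 per group, as stated. That derivation is one-sided. The sidedness of the analysis test is not stated, so two-sided 0.0125 is assumed below.

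**Arm sizes.** Assume 30% loss in one arm and 10% in the other, averaging the planned 20%: 167 × 0.7 ≈ 117 and 167 × 0.9 ≈ 150.

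**SD ratios.** Suppose a fraction p of Mindset participants take up the program and each gains 26/p PASE points, independently of background change. The mean effect is then 26, the added variance is 26²(1−p)/p, and the SD ratio is √(1 + 26²(1−p)/(p × 70.28²)).
- p = 0.50 (52 points each): √(1 + 676/4939) = 1.07.
- p = 0.25 (104 points each): √(1 + 2028/4939) = 1.19.
- A ratio near 1.3 needs about 17% uptake at over 150 points each. A ratio near 1.5 needs about 10% uptake at about 260 points each.

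**Error of the pooled test.** Let m be the smaller arm, n the larger, and r the SD of the smaller arm divided by that of the larger (larger arm's SD set to 1).
- Pooled variance: [(m−1)r² + (n−1)]/(m+n−2).
- Estimated SE: √(pooled variance × (1/m + 1/n)).
- True SE: √(r²/m + 1/n).
- k = estimated SE / true SE. The test behaves as if its critical value, 2.515 on 265 df, were 2.515k.

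For 117 vs 150 at r = 1.19, the pooled variance is (116 × 1.416 + 149)/265 = 1.182. The estimated SE is √(1.182 × 0.01521) = 0.1341 and the true SE is √(0.01210 + 0.00667) = 0.1370. So k = 0.979, the effective critical value is 2.462 and the error is about 0.0145.

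| r (smaller/larger arm) | k | effective critical value | approx. error |
|---|---|---|---|
| 1.00 | 1.000 | 2.515 | 0.0125 |
| 1.07 | 0.992 | 2.494 | 0.013 |
| 1.19 | 0.979 | 2.462 | 0.0145 |
| 1.3 | 0.969 | 2.436 | 0.0155 |
| 1.5 | 0.953 | 2.398 | 0.017 |
| 1/1.3 | 1.032 | 2.596 | 0.010 |
| 1/1.5 | 1.049 | 2.638 | 0.009 |

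Simulation with 1,000,000 trials per case agrees (for example 0.0174 at 1.5 and 0.0090 at 1/1.5).

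**Sensitivity to imbalance (simulated).**
- 134 vs 134: 0.0124 to 0.0127 at every ratio from 0.67 to 1.5.
- 125 vs 142 (25% vs 15% loss): 0.0138 at ratio 1.25 and 0.0147 at 1.5.
- 109 vs 159 (35% vs 5% loss): 0.0164 and 0.0203.

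**Family-wise bound.** If only the two No-Intervention tests are affected at 117 vs 150, the Bonferroni bound of 0.05 becomes 2 × 0.0145 + 2 × 0.0125 = 0.054 at ratio 1.19, and 2 × 0.017 + 2 × 0.0125 = 0.059 at ratio 1.5.

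**Welch's test.** Simulated error was 0.0123 to 0.0127 in every case. Power at a 26-point difference with equal variances, Welch vs pooled, was 71.6% vs 71.7% at 139/139, 68.6% for both at 117/150, and 67.6% vs 67.7% at 109/159.

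**The case against.** The strongest reply is that both conditions are assumed. The plan states only an overall dropout rate and one SD per outcome. A common variance is an explicit assumption that matches the power derivation, so there is no contradiction. This stands, and it is why the result is stated as conditional.

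Three further objections also stand in whole or part.
- If the program affects nobody, randomisation makes the change distributions the same before dropout, so the pooled test is valid. If some people benefit and none are harmed, the mean difference is not zero and a rejection is not a false positive. Inflated type I error therefore needs a zero mean difference together with unequal spread, or selective dropout that produces it. Away from the null, what remains is a misstated standard error.
- Losing many Mindset participants may remove the non-engagers who would have widened that arm's spread. The offset is only partial, because finishing the program is not the same as changing behaviour.
- At 30% vs 10% loss, selection from removing non-completers would be the larger problem, and Welch's test does nothing for it.

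A reader might infer that all four 0.0125 tests have the wrong level. The documents do not support that: Education is matched to Mindset in duration and attention and has the same one-week window, so two of the four tests are little exposed. Nor do they support saying that reported between-arm intervals will be wrong, since the 95% intervals specified are for mean change and no between-arm interval is planned.

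**Conclusion.** The point holds as a minor one. The plan fixes an equal-variance test without support or fallback, in a design where completer numbers and spread could both differ between Mindset and No-Intervention. At 117 vs 150 completers, the spread implied by 25% to 50% uptake moves 0.0125 to between 0.013 and 0.0145. Ratios of 1.3 to 1.5 give 0.0155 to 0.017, but need improbably concentrated benefit for a mean effect of 26 PASE points. The reverse pattern makes the test conservative, at 0.009 to 0.010. If either arm sizes or variances are equal, nothing changes.

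All of this rests on assumed arm sizes, assumed SD ratios, roughly normal changes and a two-sided test. A reader might go further and conclude that the trial's false-positive rate is materially inflated. The documents give no SDs or dropout by arm to support that, and the direction could be either way.

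**What to change.** In Statistical Methods, delete the equal-variance sentence and replace the pooled statistic with Welch's t-test (separate variances, Satterthwaite degrees of freedom) for the between-arm comparisons of change. Use the same standard error for any between-arm interval that is reported, and state whether the tests are one- or two-sided.

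The cost is a short edit to the section, at most about 0.1 percentage point of power when variances are equal, and no new software, since R is already named. Making the change before the data are seen also avoids choosing the test after looking at the variances. Bias from removing non-completers needs its own remedy.

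### Cheap improvement, not an error: Holm's step-down procedure, in place of single-step Bonferroni for the four one-month tests, would raise power when more than one effect is real

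*Combined protocol and SAP*

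**What the plan says.** The Statistical Methods section plans pooled-variance t-tests on the changes and then states: "We will perform Bonferonni correction for the four comparisons". The family is given by example, ending with "the mindset group vs. the no-intervention group for pain and physical activity at one-month follow-up", and the resulting threshold is 0.0125 for each test. No step-down procedure appears anywhere. The section does not say whether the t-tests are one- or two-sided. For precision it promises 95% intervals on the changes, with no multiplicity adjustment stated.

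The Sample Size section describes the same structure, "leading to four distinct comparisons", at an overall 5% level, "aiming for an 80% probability of discerning a noticeable improvement in delta". It adds: "A 26-point difference in PASE was selected as the target delta". It names 2 NRS points as the pain difference of interest. The intervention "will be deemed successful if enhancements in either or both key outcomes" are seen. The a priori power analysis in that section uses a one-sided alternative.

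Hypothesis 2, under Research Hypotheses, is wider than that success rule. It claims both less pain and more activity, against both the education and the no-intervention groups.

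**The concern.** Under single-step Bonferroni each comparison must reach 0.0125 whatever the other three show. Holm orders the four p-values and tests them at 0.05/4, 0.05/3, 0.05/2 and 0.05, stopping at the first failure. Once one null hypothesis has been rejected, fewer remain to protect, so the later thresholds can be larger with the same family-wise guarantee.

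Hypothesis 2 makes four separate claims, which will be read one by one and together. If the intervention works on more than one of them, Bonferroni will miss real differences that Holm would declare at the same 5% error. What is at stake is power on the individual and joint claims. Validity is not in question.

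**Working it through.** **Inputs from the plan.** Sample Size section: SD 70.28 (PASE) and 1.67 (pain); target 26 PASE points; 2 NRS points for pain; presumed standardised effect 0.3; 80% power; 139 per group. Statistical Methods section: threshold 0.0125.

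**Inputs assumed.** The documents give no correlation between PASE change and pain change; 0.2 is used, and 0 to 0.5 was tried. The correlation between the two contrasts on one outcome is 0.5, because they share the mindset arm and the arms are equal in size. Effects are taken as equal against both comparators unless stated. Test statistics are treated as normal.

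**Reproducing the plan's figures.** Threshold: 0.05/4 = 0.0125. Sample size, from the plan's own formula at one-sided 0.0125:

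n = 2 × 70.28² × (2.241 + 0.842)² / 26² = 138.9, so 139 per group, as stated.

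The alternatives do not match: two-sided 0.0125 gives 163, two-sided 0.05 gives 115, one-sided 0.05 gives 91. So the sample size already pays for the Bonferroni threshold.

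**Power under Bonferroni.** Power = Φ(d × √(n/2) − z), with √(139/2) = 8.337 and z = 2.241 one-sided or 2.498 two-sided.

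- PASE, d = 26/70.28 = 0.370: 0.370 × 8.337 = 3.084, giving Φ(0.843) = 80% one-sided and Φ(0.586) = 72% two-sided.
- Pain, d = 2/1.67 = 1.20: power is practically 100%.
- d = 0.3: 0.3 × 8.337 = 2.501, giving Φ(0.260) = 60% and Φ(0.003) = 50%.

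**Holm's thresholds.** 0.0125, 0.0167, 0.025, 0.05. The first equals Bonferroni's and the rest are larger, so every Bonferroni rejection is also a Holm rejection. If no p-value reaches 0.0125, neither method rejects anything.

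**Simulation.** Both procedures were applied to the same sets of four correlated test statistics, 139 per arm. Each cell shows Bonferroni → Holm.

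| True effects | Quantity | One-sided | Two-sided |
|---|---|---|---|
| PASE 26 and pain 2, both comparators | each PASE comparison | 80% → 91% | 72% → 85% |
| same | each pain comparison | 100% → 100% | 100% → 100% |
| same | all four won | 69% → 87% | 58% → 78% |
| 0.3 SD on all four | each comparison | 60% → 71% | 50% → 59% |
| PASE 26, both comparators; no pain effect | each PASE comparison | 80% → 82% | 72% → 74% |
| PASE 26 on one comparison only | that comparison | 80.0% → 80.1% | 72.1% → 72.2% |
| any of these | at least one win | unchanged | unchanged |

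The first scenario shows how the gain arises. Both pain tests are won almost surely, so the two PASE p-values then face 0.025 and 0.05 instead of 0.0125. Moving the PASE–pain correlation between 0 and 0.5 changes the per-comparison figures in the table by about one point at most.

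**Error rate.** With no effect anywhere, family-wise error is between 4.3% and 4.7% over these correlations, identical for the two methods. Holm's 5% bound holds under any dependence.

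**The case against.** The strongest objection is that nothing here is wrong. Bonferroni is pre-specified and valid, its threshold is computed correctly, and the sample size was built on it. That stands: this is an optional gain in efficiency.

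A second objection concerns the success rule. If either-or-both means at least one of the four tests, Holm adds nothing, because its first step is the same 0.0125 test. That also stands. The gain is confined to the separate and joint claims of Hypothesis 2.

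Third, a reader might infer that Holm raises power for every comparison at no cost. The figures do not support this. A comparison gains only when others are also rejected, and pain at 2 points has no room to gain. If effects exist only against no intervention (0.37 SD on PASE, 0.3 SD on pain), the one-sided gains are 80% to 82% and 60% to 64%. There are costs too. Bonferroni has matching simultaneous intervals (1 − 0.0125 = 98.75%) and Holm has no simple equivalent. True-null comparisons are also rejected somewhat more often once others succeed: for the null pain tests when PASE is real, about 1.3% to 2.6% one-sided, still within the 5% family-wise limit. The interval cost is small here, since the plan promises only 95% intervals with no adjustment stated.

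Fourth, a reader might take 0.3 SD as the plan's pain target and quote a gain for pain on that basis. The Sample Size section gives 0.3 as a general presumed effect; its stated difference for pain is 2 points, or 1.20 SD.

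**Conclusion.** A worthwhile, inexpensive improvement to a valid plan. Holm gives the same 5% family-wise protection, never loses a Bonferroni rejection, and raises power when more than one effect is real. The size depends on the other effects: about 11 points per PASE comparison one-sided (91 − 80) or 13 two-sided (85 − 72) at the plan's stated targets, about 2 points if pain does not respond, and about zero for a lone effect.

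If the final t-tests are two-sided, which the plan leaves open, Bonferroni gives 72% for PASE against the 80% aimed for. Holm then recovers the shortfall only if pain also responds.

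The larger figures rest on equal effects against both comparators, 139 analysed per arm and an assumed PASE–pain correlation, to which they are not sensitive. The documents do not support reading this as a flaw in the correction, as a higher chance of at least one significant result, or as a remedy for the post-intervention mindset outcomes. Those are also labelled primary but lie outside the four named tests.

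**What to change.** Keep the definition of the family in Statistical Methods and change only the procedure, before anyone sees results by group. Suggested wording:

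> The one-month comparisons of mindset with education and of mindset with no intervention, each for NRS pain and for PASE, form one family of four. Their p-values will be ordered and tested by Holm's procedure at 0.0125, 0.0167, 0.025 and 0.05, stopping at the first non-significant result. Holm-adjusted p-values will be reported.

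A replacement that mentions only four p-values would lose the definition of which tests are covered. State in the same place whether the tests are one- or two-sided, since the power figures depend on it.

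Leave the sample size unchanged. The cost is one sentence and one line of R code. The planned unadjusted 95% intervals would stand beside the adjusted p-values, with a note that they are not simultaneous and may not match every Holm decision. If results by group are already known, Bonferroni should remain the primary rule and Holm be shown as supplementary.
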